**Attachments**

Attach Type	File Name
Study Drug Form	Study Drug Form - Updated September 3 2019.pdf

Study Title: Marijuana Effects on Simulated Driving Performance

Institution/Site:	University of Kentucky
Document (Approval/Update) Date:	IRB 12/26/23
NCT Number:	NCT03699540
IRB Number	43636
Coversheet created:	4/29/24

Statistical Analysis Plan

All analyses will be conducted using SAS Version 9.3 or higher (SAS Institute, Inc; Cary, NC, USA), and all hypothesis testing will be two-sided with a significance level of 0.05. P-values will be presented with 3 decimals and p-values that are less than 0.001 will be represented as <0.001.

Continuous data will be summarized using descriptive statistics: number of observations (n), arithmetic mean, standard error, minimum, and maximum. Frequencies and percentages will be used to summarize categorical (discrete) outcomes. Means and standard errors will be presented to two decimal places.

Demographics and Other Baseline Characteristics

Demographic and baseline characteristics will be summarized; no statistical comparisons will be made on demographic or baseline characteristics. The demographic and baseline characteristics will consist of age, sex, race, ethnicity, height (cm), weight (kg), and BMI (kg/m²).

Continuous variables (age, height, weight, BMI) will be summarized by n, mean, standard deviation, min, median, and max. Frequencies and percentages will be used to describe categorical (discrete) variables including gender, race, and ethnicity.

Analysis of Primary Outcomes

The primary Emax for Standard Deviation in Lane Position (SDLP: amount of weaving/swerving of the car in and out of the lane) and will be analyzed in a mixed model including the nine drug conditions with a compound symmetry covariance structure. Within each model, subject will be treated as random effects, and the remaining parameter as fixed effects. Mixed models are suited for data with repeated measures, correlations among observations within an individual subject, and the presence of missing data. The response of individual subjects is first modeled, and then the estimates for each individual are combined in a group analysis (Singer, 1998; Ballinger 2004; Diggle et al. 1996; Gibbons et al. 1993; Kreft and De Leeuw 1998). Tukey post-hoc tests will compare active doses to placebo and other relevant active dose comparisons.

Analysis of Secondary Outcomes

Secondary outcomes will include:

- Raw time course data on driving performance (e.g., SDLP, number of lane changes, speed, number of collisions), driving VAS (e.g., driving difficult, drive

safely), drug VAS items (e.g., High, Good Drug Effects, Bad Drug Effects), subjective alcohol adjectives, mood scale, street value, observer adjectives, DSST, circular lights, heart rate, systolic blood pressure, diastolic blood pressure, respiration rate, and oxygen saturation from the nine dose conditions.

- Emax and Emin (where appropriate) on driving performance, drug VAS items, subjective alcohol adjectives, mood scale, street value, observer adjectives, DSST, circular lights, heart rate, systolic blood pressure, diastolic blood pressure, respiration rate, and oxygen saturation from the nine dose conditions.
- Secondary analyses will be completed in mixed models that include drug condition and time (when appropriate with an autoregressive covariance structure) with a compound symmetry covariance structure. Subject will be treated as random effects and the remaining parameters fixed. Tukey post-hoc tests will compare active doses to placebo and other relevant active dose comparisons.

Safety and Tolerability Analyses

Adverse events (AEs) recorded after signing informed consent but prior to the first dose will be recorded as baseline AEs and will be listed by subject but will not be included in the summary safety analysis. AEs will be summarized by relationship to study drug and severity.

Missing Data

Within-session missing data are expected to be less than 3% for each outcome. Inspection of missing data and correlates of missingness will be examined upon study completion. The use of mixed models as an analytic strategy obviates the need for the missing values to be imputed.

Identification and Summary of Protocol Deviations

Major protocol deviations from the participant's entry criteria through study completion will be documented and summarized as far as they can be extracted from the numeric and coded study data.

References:

Ballinger GA (2004) Using generalized estimating equations for longitudinal data analysis. *Organizational Research Methods* 7(2): 127-150.

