- A compelling rationale for proposed exclusion of any sex/gender or racial/ethnic group;
- Justification for the inclusion of vulnerable groups such as children, prisoners, adults with impaired consent capacity, or others who may be vulnerable to coercion or undue influence.

Please consider these resources:

[NIH Diversity Policy](#)

[FDA Diversity Guidance](#) 

Our goal is to have up to 24 volunteers complete the study. Based on previous studies our research group has completed at UK, we anticipate that we will have up to 100 subjects sign consent in order to complete this study. Written, sober informed consent will be obtained prior to enrollment, and subjects will be paid for their participation.

Inclusion criteria include: 1) male and female English-speaking literate adults, ages 21-50 years old, 2) current recreational marijuana use (range: approximately 2 occasions in the past 3 months; through everyday users); history of vaporized or smoked marijuana use, 3) observed urine sample testing positive for cannabinoids (e.g., THC), 4) current weekly drivers with a history of at least 2 years of driving, 5) current alcohol use of less than or equal to 12 out of the past 30 days, 6) history of drinking to intoxication or impairment; history of using marijuana to intoxication or impairment, 7) not seeking treatment for drug or alcohol use, 8) if female, a negative pregnancy test and use of effective form of contraception during study participation (e.g., oral contraceptive, abstinence, barrier method), and 9) valid driver's license.

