Due to the double-dummy design of this study, both vaporized marijuana and a cocktail will administered during each session. The vaporized dose will contain an active dose of marijuana or placebo. Cocktails will be comprised of an oral solution containing alcohol (0.8 g/kg, mixed with juice) or placebo (a very small amount of alcohol to mask the placebo). Active marijuana and active alcohol doses will not be administered in combination.

Healthy volunteers will participate in a total of 5 experimental sessions. During each session, the doses will be administered under double-blind conditions, and data will be collected for approximately 8 hours post-dose. Each session is designed to collect an array of multi-dimensional data, including subjective effect questionnaires of positive and negative mood, observer ratings, physiological measures, driving simulator performance and cognitive tasks (see below under Outpatient Research Procedures for further detail).

Attachments

Attach Type	File Name
StudyDesign	Screening Packet.pdf

Subject Recruitment Methods & Advertising

Describe how the study team will identify and recruit subjects. Please consider the following items and provide additional information as needed so that the IRB can follow each step of the recruitment process.

- How will the study team identify potential participants?
- Who will first contact the potential subjects, and how?
- Will you use advertisements? If so, how will you distribute those?
- How and where will the research team meet with potential participants?
- If applicable, describe proposed outreach programs for recruiting women, minorities, or disparate populations.
- How you will minimize undue influence in recruitment?
- Attach copies of all recruiting and advertising materials (emails, verbal scripts, flyers, posts, messages, etc.).

For additional information on recruiting and advertising:

- [IRB Application Instructions - Advertisements](#)
- [PI Guide to Identification and Recruitment of Human Subjects for Research](#)

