All volunteers receive medical and psychiatric screening and examination prior to study participation, including: 1) history and physical examination by a physician, 2) Beck Depression Inventory (screens for depression), 3) Symptom Checklist-90 (general psychiatric symptom inventory), 4) electrocardiogram, 5) laboratory testing (complete blood count with differential, complete metabolic panel, urinalysis with microscopic evaluation, urine drug testing, and urine pregnancy test for females), 6) literacy assessment and 7) evaluation of drug and alcohol use histories. Only those in good medical and psychiatric health, as determined by the study physician, are allowed to participate. Once a person meets inclusion/exclusion criteria, they will be permitted to begin participation in experimental study sessions.

General Methods: Participants will complete one to three training sessions to familiarize them to the driving simulator, the vaporizer procedure (using placebo marijuana), and the various computer tasks to insure that they are comfortable with the equipment and tasks prior to data collection. To familiarize participants with the smoking procedure, placebo marijuana will be administered; participants will be told that the vaporized dose is placebo. After this training is complete, the experimental sessions will be initiated.

Participants will complete a total of 5 experimental sessions. During each session, a battery of assessments will be conducted prior to (as a baseline evaluation) and at regular intervals 8 hours post marijuana dose. These assessments will include an array of subjective, cognitive and psychomotor tasks, driving simulator performance tasks and physiological assessments. The presentation of these assessments is based on the time-active curves for the drugs being tested. On session days, participants will arrive at the laboratory at approximately 9:00 am and will be scheduled to discharge at approximately 6:00 pm (total participation time will be approximately 9 hours).

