The content and flow of experimental sessions are designed to capture the time-action curves for the test agents at the selected doses (peak subjective effects of high potency marijuana ~ 15 mins – 3 hrs (Haney et al., 2016; Hunault et al., 2014; Ramaekers et al., 2006) alcohol (0.8 g/kg) ~ 15 min – 3 hrs (Kirkpatrick & de Wit, 2013)). The oral alcohol solution will be administered 15 minutes prior to smoked marijuana; however, only one agent will be active (i.e., active alcohol + placebo marijuana; active marijuana + placebo drink). Participants will vaporize marijuana (approx. 166 mg total weight). Driving simulation will be tested at six time points during each test session at baseline, 15 min and 1, 2, 4, and 6 hr post-marijuana dose. This will allow us to examine the driving ability 1) immediately after smoking (15 min), 2) during peak subjective ratings of feeling high (15 mins-2 hrs), (Hunault et al., 2014; Ramaekers et al., 2006) and 3) after subjective intoxication has subsided, but while sedation is expected to remain elevated (6 hrs). (Hunault et al., 2014)

Participants are required 1) to successfully complete a field sobriety test, 2) have a BAC = 0.02, and 3) report no acute intoxication in order to be discharged from the session. Free round-trip transportation will be provided for subject safety (e.g., taxi). Participants are not permitted to transport themselves home.

Study Drug

All drug doses will be stored at the UK Robert Straus Research Facility under secure conditions specially equipped for Schedule I drug storage. Doses will be blinded by the University of Kentucky (UK) Investigational Pharmacy licensed pharmacists (Drs. [name], [name]). Marijuana will be obtained through the NIDA drug supply. Each vaporized dose will contain approximately 166 mg of plant material. Research Triangle Institute (RTI) will provide chemical analysis reports of marijuana cannabinoid concentrations with each lot of marijuana, which will be reviewed by the PI for consistency. A Volcano brand vaporizer will be used to deliver the doses. This model has been used in several studies (e.g., Spindle et al., 2018; JAMA) and is more efficient delivery system than a marijuana cigarette (drug is lost through combustion and side stream smoke; a vaporizer is a closed system that eliminates these

concerns). Alcohol doses (USP-grade ethanol, juice mixer) and placebo drinks (juice with 1% alcohol) will be prepared by the pharmacists.

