Randomized orders will be generated by the statistician. All dosing will be double-blind; however, sealed dose orders will be available on-site and at the pharmacy in the event of an emergency. The drug formulation plans for these studies will be reviewed by the FDA before study initiation. The IND will be submitted after we obtain IRB approval.

Dose Selection

The doses of vaporized marijuana were selected as representative recreational and medicinal marijuana strains that are currently legally available in dispensaries across the U.S. (360, 2017; Sevigny, Pacula, & Heaton, 2014). Strains with 1) high THC/trace CBD, 2) high THC/moderate amounts of CBD are used for medicinal and recreational use (2:1 ratio), and 3) moderate amounts of THC alone (trace CBD) are all used for both medical and recreational purposes. (Lankenau et al., 2016; MA, 2014; Ko, Bober, Mindra, & Moreau, 2016; Kolikonda et al., 2016; Maa & Figi, 2014; 360, 2017; Belendiuk, Babson, Vandrey, & Bonn-Miller, 2015; Freeman & Winstock, 2015; Sevigny et al., 2014).

These doses will provide information regarding the effects of 1) a high dose of THC alone (approximately 30 mg vaporized THC), 2) a moderate dose of THC with CBD (approximately 15 mg THC + 7.5 mg CBD), and 3) moderate dose of THC (approximately 15 mg THC) allowing assessment of a two-fold dose range of THC compared to placebo marijuana (0 mg THC, 0 mg CBD) and will provide some information about the effects of THC combined with CBD. Comparator conditions of doses of CBD alone, or assessments of THC/CBD interactions will not be included in this small-scale exploratory study. The risk of lung infection from vaporized marijuana is stated in the consent form.

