The oral solution (e.g., ~16 oz. drink [450 mL/70 kg]) will contain alcohol (0.8 g/kg) or placebo. Placebo is comprised of juice with a very small amount of alcohol (~3mL or approx. 1% alcohol) floated on top of the drink which produces a scent of alcohol, but does not increase breath alcohol levels. Female participants will receive an alcohol dose that is 15% less than the dose administered to men. This allows for comparable breath alcohol concentrations in men and women (as it helps account for differences in body fat and body water). The alcohol solution will be split into three aliquots contained in an opaque covered cup with a straw. Participants will be asked to complete the alcohol solution in 15 minutes (e.g., approx. 5 minutes per aliquot). The active alcohol solution will produce a breath alcohol level of approximately 0.08 within approximately half hour of administration (Kirkpatrick & de Wit, 2013).

Outpatient Methods

For each experimental session, participants will arrive at the laboratory in the morning having abstained from alcohol for 24 hrs, cigarettes and caffeine for 8 hrs, and having fasted (water permitted, no food) since waking. Session will be conducted if urine samples test negative for drugs of abuse (aside from THC) and pregnancy in females; breath samples must test negative (0.000 BAC) for alcohol and cigarette/marijuana smoking abstinence will be confirmed (below approximately 15 PPM CO). After CO is confirmed to be below the cut-off, cigarette smoking and coffee (with standardized caffeine content) will be permitted 1 hr before dosing and after session (we have previously used similar models for marijuana and alcohol studies. A standardized breakfast will be provided approximately 1 hr prior to dose administration.

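### The primary SDLP Emax model leaves out the pre-dose SDLP collected at every session and may give up precision that could be had at almost no cost

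*SAP*

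**What the plan says.** The SAP's Analysis of Primary Outcomes puts SDLP Emax into a mixed model with drug condition and a compound symmetry covariance, and adds: "Within each model, subject will be treated as random effects, and the remaining parameter as fixed effects". The fixed parameter is in the singular, and condition is the only candidate named. There is no pre-dose covariate, change from baseline, or session term. The secondary models add time only. The protocol's Data and Safety Monitoring section mentions mixed models and other analyses in general terms and names no covariate.

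The protocol does collect the measurement. Under General Methods: "Driving simulation will be tested at six time points during each test session at baseline, 15 min", followed by four later post-dose drives. The same section says of each session that "a battery of assessments will be conducted prior to (as a baseline evaluation) and at regular intervals" after dosing.

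The design is a crossover: "Healthy volunteers will participate in a total of 5 experimental sessions" (Study Design), "Randomized orders will be generated by the statistician" (Study Drug), and "Our goal is to have up to 24 volunteers complete the study" (Study Population).

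Neither document defines Emax.

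**The concern.** A random subject effect with compound symmetry removes only what is constant for a person across sessions. If a participant drives worse on one day than another for reasons unrelated to the dose, that difference enters the residual of every contrast involving that day. A drive taken before dosing on the same day is the natural measure of it.

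Outpatient Methods restricts the sources of such variation through abstinence from alcohol, cigarettes and caffeine, fasting, a carbon monoxide cut-off and a fixed meal ("A standardized breakfast will be provided approximately 1 hr prior to dose administration"). It does not remove them, because "cigarette smoking and coffee (with standardized caffeine content) will be permitted 1 hr before dosing". The documents do not say whether the pre-dose drive comes before or after that point, so it may reflect only part of the day's variation.

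What is at stake is power for the primary contrasts with at most 24 completers. The undefined Emax is tied to this: until the SAP says whether the pre-dose drive is among those searched for the maximum, its role as a covariate is not settled.

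**Working it through.** Neither document gives a power calculation, SD, correlation or effect size for SDLP, so there is no figure to reproduce.

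**Inputs from the documents.** 24 completers; five sessions, taken as five conditions; one pre-dose and five post-dose drives per session; two-sided 0.05; Tukey contrasts; condition fixed, subject random.

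**Assumptions.** Within-subject SD of a single drive = 1. A share *s* of that variance is common to all drives in a session. Active effect 0.9 SD at 15 min to 2 h, half of that at 4 h, none at 6 h. No drift over sessions.

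**Step 1, general relation.** Unadjusted SE of a contrast = σ√(2/24) = 0.289σ, where σ is the residual SD of Emax. Residual df = (24 − 1)(5 − 1) = 92, and the Tukey critical t is 2.783. A covariate with within-subject correlation ρ to Emax multiplies the SE by √(1 − ρ²), and the equivalent gain in sample size is 1/(1 − ρ²) − 1. For ρ = 0.1, 0.3, 0.5 and 0.7 the SE factors are 0.995, 0.954, 0.866 and 0.714, and the gains 1%, 10%, 33% and 96%.

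**Step 2, link to the session share.** With no drug effect, the simulated variance of the maximum of five independent drives is 0.446. Therefore:

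- Emax variance, condition only: s + 0.446(1 − s)
- with the pre-dose covariate (covariance s, covariate variance 1): subtract s²
- with only half of the session variance shared by pre-dose and post-dose drives: covariance s/2, so subtract s²/4
- with pre-dose SDLP subtracted from Emax: 1.446(1 − s)

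At s = 0.4 these are 0.4 + 0.268 = 0.668; 0.668 − 0.160 = 0.508; 0.668 − 0.040 = 0.628; and 0.868. Subtraction is worse than no adjustment until s reaches 0.5.

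**Step 3, simulation** (40,000 trials per cell; Monte Carlo SE of a power at most √(0.25/40,000) = 0.0025; fixed subject effects). Equivalent completers = 24 × variance ratio.

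| Share s | Power, condition only | Power, with pre-dose | Contrast SD, condition only / with pre-dose | Variance ratio | Equivalent completers |
|---|---|---|---|---|---|
| 0 | .793 | .786 | .1953 / .1964 | 0.989 | 23.7 |
| 0.1 | .737 | .742 | .2061 / .2055 | 1.006 | 24.1 |
| 0.2 | .693 | .724 | .2174 / .2113 | 1.059 | 25.4 |
| 0.4 | .601 | .748 | .2372 / .2093 | 1.284 | 30.8 |
| 0.6 | .550 | .867 | .2566 / .1904 | 1.816 | 43.6 |

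With half capture, power without/with the term is .739/.735, .689/.691, .610/.637 and .550/.614 at shares 0.1, 0.2, 0.4 and 0.6.

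At shares 0, 0.2 and 0.4 (10,000 trials), an effect of 0.7 SD gives .494/.488, .390/.420 and .327/.444; an effect of 1.1 SD gives .953/.949, .900/.920 and .845/.932.

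**Step 4, definition of Emax.** If the pre-dose drive is also searched, the active-placebo contrast at share 0 falls from 0.71 to 0.64 SD. Condition-only power becomes .703, .591, .504 and .466 at shares 0, 0.2, 0.4 and 0.6.

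**Step 5, bias.** With no drug effect, the mean contrast is within 0.003 SD of zero in both models at shares 0 and 0.4, and a single contrast is rejected at .006 to .007.

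**Step 6, form of the covariate.** In a REML random-intercept check (share 0, participant SD 1, 400 trials) the mean SE was .196 for condition only, .201 with session pre-dose alone, and .198 with session pre-dose plus the participant's mean. The participant mean keeps the adjustment within person.

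**The case against.** The condition-only model is a valid analysis of a randomized crossover. Nothing is biased, so this is an efficiency choice and not an error. That stands.

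The gain also rests on a quantity the documents do not supply. Up to a share of 0.2 the term is worth between about −1 and +3 points of power, and with half capture it is worth about nothing there. Gains of 15 or 32 points need a share of 0.4 or 0.6 and full capture by one drive of about 10 minutes, and the session-day controls give reason to doubt a large share. That stands too, and no large loss should be claimed.

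The simulation leaves out differences between people in drug response, which are plausible because enrollment ranges from infrequent to daily users. With an assumed person-by-condition SD of 0.5 and full capture (8,000 trials), power without/with the term is .58/.61, .51/.63 and .47/.75 at shares 0.2, 0.4 and 0.6, and the equivalent completers at 0.6 drop from about 44 to about 39. The gains shrink but do not vanish.

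At low shares the definition of Emax matters more than the covariate. That is fair, and the fix settles both.

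Finally, if Emax meant peak change from baseline, the pre-dose drive would already enter through the outcome. No text says so. That reading would strengthen the case for a covariate: peak change gives power of .22 against .79 at share 0, and .71 against .87 at share 0.6.

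**Conclusion.** The concern holds. As written, the primary model does not use a pre-dose SDLP that is measured at every session, and any session-level variation stays in the residual of each contrast. The consequence is possible loss of precision, without bias.

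Its size is unknown. Under the stated assumptions it is nil at a session share of 0 to 0.1, about 3 points of power at 0.2 and about 15 at 0.4. It falls to about 0 and 3 points at 0.2 and 0.4 if the pre-dose drive captures only half of the variation. These values are illustrative and are not bounds.

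The case for change rests on the asymmetry. The worst simulated cost of the term is under one point of power (.793 to .786), while the possible gain is material with at most 24 completers. The missing definition of Emax is a gap whatever the session share: in the condition-only model it is worth 9 to 10 points at shares 0 to 0.4. The change is recommended; the planned analysis would not be invalid without it.

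**What to change.** Put the following in the SAP before unblinding:

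> Emax is the highest SDLP among the five post-dose drives of a session; the pre-dose drive is not searched. Fixed effects are condition, that session's pre-dose SDLP and the participant's mean pre-dose SDLP; participant is random. The condition-only model is reported as a sensitivity analysis.

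Use the pre-dose value as a covariate and do not subtract it.

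Session number as a further fixed effect is optional because it is a trade-off. In 10,000-trial runs at shares 0, 0.2 and 0.4, adding it to the pre-dose term moved power from .794 to .769, .729 to .699 and .755 to .729 without drift. With a drift of 0.1 SD per session the moves were .761 to .766, .717 to .705 and .747 to .734.

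The cost is SAP wording and about 2 degrees of freedom, with no new data. The SAP's nine conditions and the protocol's five sessions must be reconciled separately.

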We have developed driving scenario courses with comparable variables and construct characteristics for use in repeated testing designs. These driving scenarios are approximately 10 minutes in length and include various highway and city driving courses. We are familiar with the consensus recommendations from the International Council on Alcohol, Drugs & Traffic Safety's (ICADTS) for behavioral outcomes in drugged driving studies and will focus on those outcomes most commonly evaluated in driving simulator studies, for example, lateral position variability (i.e., a marker of lane deviation and tactical measures (deceleration maneuvering in response to an obstacle or yellow light). However, other variables will be explored.

Data will be collected for approximately 8 hours post-dose (e.g., relative to marijuana administration) and we expect total session participation time will be approximately 9 hours. A field sobriety test will be completed in the presence of an investigator or senior staff member before participants will be released to go home. If the participant exhibits signs of impairment, they will be retained at the laboratory and re-assessed every 20 minutes (and paid a rate of \$10/hr for this extra time). In our experience, the effects of marijuana are minimal at 8 hours post-dose and breath alcohol levels should be 0.00 – 0.02 at this time. Participants will not be permitted to transport themselves home under any circumstance. We will provide transportation (for example: taxi, Uber, similar car service). Alternatively, a participant can arrange for a friend/family member to provide transportation if they choose. We will also advise participants not to use drugs or alcohol on the day of session (either prior to or after the session has been completed) and not to drive a car or operate machinery for the remainder of the day. We have successfully administered smoked marijuana and alcohol on an outpatient basis using similar methods (Protocols #15-0976-F3R, #14-0769-F3R, #11-0100-F6A).

Sessions in which active drug doses are administered will be followed by at least one wash-out day prior to the next session (e.g., minimum of 48 hours between doses).

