Data Safety and Monitoring Plan: Data will be collected using a computerized data collection and management system wherever possible. This system automates the collection of data, which ensures the accuracy and completeness of data collection. The data are stored in a unique file on the hard drive of the computer and are printed after all the tasks are completed. In all instances, the data files do not contain the name of the subject; but instead, a unique eight-digit number identifies each subject. A computer file linking the unique number with the subject's name will be kept on a stand-alone, password-protected encrypted computer. All data requiring hand entry (e.g., urinalysis results) will be double entered by two separate staff members and comparison macros conducted to ensure accuracy. Data files for experimental tasks and physiological measures from each experimental session will be manipulated and combined into a single electronic spreadsheet for each subject by the statistician. Data for all volunteers will then be combined into a single electronic spreadsheet and separated by experimental measure for statistical analysis. The primary outcome measures will include driving performance on key measures (e.g., SDLP, brake latency, reaction time, collisions). Secondary outcomes will include observer ratings, safety outcomes (side effects and physiological measures) and cognitive/psychomotor performance; sex differences will be explored. Data will be analyzed using LMM for repeated measures designs along with other statistical analyses. The alpha level will be set at 5%. As noted above, wherever possible, data are collected using an automated computer system, which increases the accuracy and completeness of data collection and ensures the validity and integrity of the data. The initial data manipulation described above will be conducted twice and compared. All analyses are conducted by our statistician ([name]). The quality of manipulated data and data analyses will be monitored by random inspection by the PI and/or Co-Investigators.

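### The SAP's adverse event summary has no breakdown by dose condition, so it cannot show which of the five crossover conditions reported events followed

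*SAP*

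**What the plan says.** The SAP's Safety and Tolerability Analyses section makes two provisions. Events after consent but "prior to the first dose will be recorded as baseline AEs"; these are listed by subject and kept out of the summary. For the rest, "AEs will be summarized by relationship to study drug and severity". Dose condition, session and a rule for assigning an event to a dose are not mentioned.

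The same SAP, under Analysis of Secondary Outcomes, handles other tolerability measures by dose condition. They include "drug VAS items (e.g., High, Good Drug Effects, Bad Drug Effects), subjective alcohol adjectives, mood scale, street value, observer adjectives", and also heart rate, blood pressure, respiration rate and oxygen saturation.

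The protocol (Data and Safety Monitoring) states: "Secondary outcomes will include observer ratings, safety outcomes (side effects and physiological measures) and cognitive/psychomotor performance". That section describes AE collection, weekly review and reporting of serious events, but gives no AE table. Collection runs through the whole of participation and the follow-up visit at two to four weeks.

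**The concern.** In a placebo-controlled crossover, the natural safety question is how often events followed each active dose compared with placebo in the same people. The design can address that descriptively, because each completer has a placebo session and an alcohol session as well as three marijuana sessions. A summary by relationship and severity alone drops the one label that makes the comparison possible.

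The placebo column matters more than usual here. The protocol's risk section lists headache, nausea, dizziness and vomiting as possible effects of the driving simulator itself, and every session includes simulated driving. The same section lists headache, nausea and vomiting for alcohol, and headache, dizziness and stomach upset for marijuana. Without a count by condition, a reader cannot tell whether such events were more frequent after 30 mg THC, after alcohol, or about as frequent after placebo.

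**Working it through.** The plan gives no AE figure to reproduce, so the check is mainly a comparison of texts.

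**1. Does every volunteer receive every condition?** Protocol, Objectives and Study Design: a within-subject crossover with five sessions. The conditions are 30 mg THC, 15 mg THC + 7.5 mg CBD, 15 mg THC, placebo and alcohol. The SAP speaks of nine conditions. That conflict is a separate problem, and I use the protocol's five.

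**2. Could relationship to study drug stand in for condition?** No, for three reasons.
- Protocol, Study Design: "both vaporized marijuana and a cocktail will administered during each session".
- Protocol, Study Drug Information: both marijuana and alcohol are listed as study drugs.
- Protocol, Research Procedures (Study Drug): "All dosing will be double-blind; however, sealed dose orders will be available on-site and at the pharmacy".

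The person rating causality sees a volunteer who has inhaled a vapor and finished a drink, and does not know which, if either, was active. An event rated as related could follow any of the five conditions, placebo included.

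**3. Is condition supplied elsewhere?** For the other secondary outcomes the SAP names the dose conditions and puts drug condition in the model. AEs are not on that list. The protocol's general statement that data will be analysed with linear mixed models specifies no AE table.

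**4. Which information is missing?** Vital signs, drug-effect items, mood, alcohol adjectives and observer adjectives all have analyses by condition. What remains is AEs that volunteers report or staff observe. Nausea, vomiting, headache and faintness appear in the protocol's risk section but are not named among the SAP outcomes. The SAP does not spell out every item on its adjective lists, so some overlap is possible.

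**5. How much could a table by condition show?** Inputs: up to 24 completers (Protocol, Study Population) and five sessions (Study Design).
- Dosings: 24 × 5 = 120, that is 120 / 5 = 24 per condition.
- Exact (Clopper-Pearson) 95% interval for x of n: lower limit = 2.5% quantile of Beta(x, n − x + 1), upper limit = 97.5% quantile of Beta(x + 1, n − x). For x = 0 the lower limit is 0 and the upper limit is 1 − 0.025^(1/n).

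The documents give no expected AE rate, so the event counts below are assumptions spanning a range.

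| Volunteers with an AE, of 24 | Proportion | Exact 95% interval |
|---|---|---|
| 0 | 0% | 0 to 14.2% |
| 3 | 12.5% | 2.7 to 32.4% |
| 6 | 25.0% | 9.8 to 46.7% |

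These intervals are wide. The table would describe the pattern of events and would not support formal tests.

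**6. Is the first dose defined?** Protocol, Research Procedures (General Methods): training before the experimental sessions includes vaporized placebo marijuana. The SAP's cut could therefore fall at a training dose or at the first blinded session dose.

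**The case against.** The strongest reply is that most acute tolerability information is already compared across conditions. The protocol counts physiological measurement and drug-effect questionnaires among its methods for monitoring AEs, and the SAP models both by condition with Tukey comparisons. The protocol also calls this a small-scale exploratory study, and counts of about 24 per condition settle little. The dose orders exist, so the table could be made later. All of this limits the importance of the point. It does not supply the missing breakdown for reported events, and later tabulation works only if onset times were recorded and would follow no pre-stated assignment rule.

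Four stronger readings are tempting, and the documents do not support them.

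- *The sponsor intends to pool all conditions.* The SAP does not say so. It only leaves condition out of the stated summary.
- *A single cut at the first dose wrongly treats sessions unequally, because pre-dose events are only listed in session 1 but counted in later sessions.* Counting events from the first dose onward is ordinary treatment-emergent practice, and an event before the second session's dosing does follow an earlier exposure. Which pre-dose periods fall on which side also depends on whether the training placebo counts as the first dose. What stands is that such events need a condition assigned to them.
- *Placebo sessions have a shorter observation window.* The wash-out is stated for active doses only ("Sessions in which active drug doses are administered will be followed by at least one wash-out day prior to the next session"), but nothing shows that shorter gaps are scheduled after placebo, and doing so could reveal the condition.
- *Tolerability cannot be compared between conditions at all.* The analyses of vital signs and ratings by condition contradict this.

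**Conclusion.** The point holds for reported and staff-observed AEs. Followed as written, the SAP's summary cannot show which condition an event followed. It therefore gives no descriptive comparison of these events with placebo, between the THC doses or with alcohol, although side effects are a secondary outcome. The primary analysis and the analyses of vital signs and ratings by condition are unaffected. The change is worth making because it is cheap, but it is not critical to the trial's main conclusion.

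The conclusion rests on the protocol's five conditions rather than the SAP's nine, and the precision figures assume 24 completers. The effect on reported AE frequencies cannot be estimated, because the documents give no AE rate.

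**What to change.** Add one descriptive table to the SAP's safety section.

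- **Content:** for each condition, the number of AEs and the number of volunteers with at least one AE, with volunteers dosed in that condition as denominator, split by severity and relationship.
- **Assignment:** each AE goes to the condition most recently dosed. An event before dosing on a later session day therefore belongs to the previous session's condition.
- **Timing:** show in-session events (about 8 hours after dosing in every session) as the like-for-like row. Put later between-session and follow-up events in a separate row.
- **Definition:** state that the first dose is the first blinded experimental dose, so that the training placebo does not start the count.

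The cost is SAP wording and one table. The dose orders already exist and can be merged with the AE data once the blind is lifted. AE onset time must be recorded, and the documents do not say whether the AE form captures it. Two downsides remain: counts will be small, so the table should be labelled descriptive, and some late events may be assigned to the wrong condition, which is why they belong in their own row.
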